**4) Primary Disease or Condition being studied in the trial, or the focus of the study:**  
Subclinical Depression

**5) Keywords:** Priming Stimulation, Theta-Burst Stimulation, Functional NIRS, Emotion Discrimination, Subclinical depression

**6) Primary Purpose:** Optimization of stimulation parameters for a priming stimulation protocol

**7) Study Phase:** N/A

**8) Intervention Study Model:** Parallel, sham-control

**9) Model Description:** (Objectives)

The proposed research has two primary objectives.

The first objective is to understand the effects of priming stimulation timing of the left DLPFC using fNIRS at rest. The time window between priming cTBS and test iTBS will be either 0, 10, or 20 minutes. We hypothesize that 0 minutes will eliminate the effect of the test iTBS, whereas 10 minutes will potentiate it; 20 minutes will have no effect (i.e., result in no difference, relative to sham priming).

The second objective is to evaluate the effects of priming stimulation in the context of facial emotion processing and executive function in subclinical depression. Previous evidence indicates that DLPFC stimulation modulates affective processing on the neural and behavioral level. We hypothesize that optimal priming stimulation will affect reaction times in an emotion-specific way and will reduce the negative bias observed in subclinical depression.

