### **Outcome 3: Secondary Outcome Measure**

Title: Behavioral measures including reaction times and recognition accuracy

Description: Reaction times and accuracy during the cognitive tasks will be evaluated before and after stimulation

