## **13) Statistical Analysis Plan:**

fNIRS data analysis will follow the standard processing steps. This includes spatial registration (recording of standard cranial landmarks nasion, inion, left and right ear, and the 3D locations of the fNIRS probes); transformation to MNI space [39]; band-pass

filtering for motion artifact removal; and estimation of the hemodynamic response function using GLM, as implemented in the NIRS Toolbox for MATLAB. Comparisons between baseline and task HbO will reveal task-related de/activations, corrected for multiple comparisons (52 channels). Average HbO changes will then be determined for each channel and each measurement and entered into second-level analysis. Similarly, means of HbO for pre and post-stimulation will be entered into second-level analysis.

A t-test between pre- and post-stimulation in condition 1 will be performed to test hypothesis 1. Hypothesis 1 will be supported if there is a significant increase in prefrontal HbO after stimulation.

A t-test between condition 2 and 1 using change scores will be performed to test hypothesis 2. Hypothesis 2 will be supported if there is a significant stronger change in HbO in condition 1 compared to condition 2

A t-test between condition 3 and 1 using change scores will be performed to test hypothesis 3. Hypothesis 3 will be supported if there is a significant stronger change in HbO in condition 3 compared to condition 1.

A t-test between pre- and post-stimulation in condition 4 and between change scores of condition 1 and 4 will be performed to test hypothesis 4. Hypothesis 4 will be supported if there is a significant increase in prefrontal HbO after stimulation, but no significant difference in change scores between condition 1 and 4.

Regarding the three exploratory hypotheses about participants' behavior (reaction times, hits and misses) and HbO changes during cognitive tasks, linear mixed models will be conducted to determine differences between conditions, followed by post-hoc pairwise comparisons. Here, a three-way interaction between time, condition and emotion will be evaluated and followed by post-hoc two-way interactions and pairwise comparisons.

Hypothesis E1 will be supported if there is a significant change in HbO and/or behavioral measures in condition 1 in some (e.g. sad) but not other emotions (e.g. happy) after stimulation (following a post-hoc 2-way interaction between time and emotion).

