Hypothesis E2 will be supported if there is a significant interaction between time, emotion and conditions 2 and 1.

Hypothesis E3 will be supported if there is a significant interaction between time, emotion and conditions 3 and 1.

Hypothesis E4 will be supported if there is a significant change in condition 4 in some (e.g. sad) but not other emotions (e.g. happy) after stimulation (following a post-hoc 2-way interaction between time and emotion).

Finally, two t-tests comparing ERA- recognition accuracies between subclinically depressed and control participants and between pre and post stimulation in the sample of subclinically depressed participants will be performed in order to test hypotheses E5 and E6, respectively.

Hypothesis E5 will be supported if recognition accuracy is reduced in participants with subclinical depression compared to the control sample.

Hypothesis E6 will be supported if recognition accuracy will be increased after stimulation compared to baseline in participants with subclinical depression.

Behavioral data will be analyzed using the IBM SPSS software (<http://www-01.ibm.com/software/analytics/spss/>). The alpha level will be set at 0.05, adjusted for multiple comparisons using the Bonferroni-Holm procedure. For GLM, post-hoc pairwise comparisons will be corrected using Fisher least significant difference procedure in accordance with the closed test principle, i.e., post hoc comparisons will be declared nonsignificant if the global p value of the main- or interaction effect is nonsignificant, but carried out without further correction in case of a significant global effect.

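### E1 and E4 require non-significance in other emotions, so a shift common to all emotions can hide a true emotion-specific effect

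*Combined protocol and SAP*

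**What the plan says.** Section 13 (Statistical Analysis Plan) takes HbO during the tasks and behaviour together: "Regarding the three exploratory hypotheses about participants' behavior (reaction times, hits and misses) and HbO changes during cognitive tasks". These go into linear mixed models in which "a three-way interaction between time, condition and emotion will be evaluated and followed by post-hoc two-way interactions and pairwise comparisons".

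E1 is then supported by a "significant change in HbO and/or behavioral measures in condition 1 in some (e.g. sad) but not other emotions (e.g. happy) after stimulation", with the qualifier "following a post-hoc 2-way interaction between time and emotion". E4 has the same some-but-not-others pattern and the same qualifier for condition 4, without the and/or clause. E2 and E3 are decided differently: each is supported by a significant interaction of time, emotion and the two conditions compared.

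On multiplicity, the same section says "The alpha level will be set at 0.05, adjusted for multiple comparisons using the Bonferroni-Holm procedure", directly after naming the software for behavioural data. For post-hoc tests it adds that "post hoc comparisons will be declared nonsignificant if the global p value of the main- or interaction effect is nonsignificant", and otherwise leaves them uncorrected. It does not define the Holm family, list the emotions, or say which task or behavioural measure counts for E1. Section 11 gives the behavioural outcome as "Behavioral measures including reaction times and recognition accuracy".

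**The concern.** E1 and E4 ask whether the change after stimulation differs between emotions. The time-by-emotion interaction answers that. The plan tests it, but then hands the verdict to a pattern of separate tests: significant here, not significant there. A significant change in one emotion beside a non-significant change in another is not evidence that the two differ. Equally, two significant changes are not evidence that they are equal.

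The design makes the second error likely. Each hypothesis is judged on the arm's own pre-post change. Under section 10, condition 1 receives sham priming and then active iTBS, and no arm is sham throughout. Task practice therefore enters every emotion's change in full. If practice moves all emotions enough to be significant, no emotion is left to be the non-significant one. The hypothesis is then unsupported even when the interaction is clear.

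**Working it through.** The documents give no effect size, SD, power or practice effect for E1 or E4, so there is no figure of theirs to reproduce. The following is an illustration.

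**Inputs**
- From section 10: 80 participants in 4 arms, so 80/4 = 20 per arm if allocation is equal (the ratio is not stated).
- From section 13: alpha 0.05; the time-by-emotion test first, then the pattern.
- Assumed: change scores with SD 1; correlation 0.5 between emotions; two-sided tests; one outcome; 2, 3 or 6 emotions; a true effect of +0.8 SD on one emotion (call it sad); and a practice shift *s* in the same direction in all emotions.

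**Step 1: two emotions, in closed form**
- The sad-minus-happy difference has mean (0.8 + *s*) − *s* = 0.8 and SD √(1 + 1 − 2 × 0.5) = 1. The shift cancels. The noncentrality is 0.8 × √20 = 3.58 on 19 df, giving power of about 92% whatever *s* is.
- The happy test alone has noncentrality *s* × √20. At *s* = 0.5 this is 2.24 and happy is significant in 56% of trials. At *s* = 0.8 it is 3.58 and happy is significant in 92%.
- At these shifts sad, with mean 1.3 or 1.6 SD, is almost always significant. Support therefore needs happy to be non-significant: at most 100 − 56 = 44% of trials at *s* = 0.5, and 100 − 92 = 8% at *s* = 0.8.

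**Step 2: simulation of the rule with the two-way step**

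Support means that the time-by-emotion F-test is significant, at least one emotion is significant and at least one is not. Repeated runs agree to within about one percentage point.

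| Shift common to all emotions | 2 emotions | 3 emotions | 6 emotions | Time-by-emotion test alone |
|---|---|---|---|---|
| 0 | 84% | 91% | 92% | 92-96% |
| 0.5 SD | 42% | 59% | 76% | 92-96% |
| 0.8 SD | 8% | 13% | 24% | 92-96% |

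With two emotions and a 0.8 SD shift, about 85% of trials have a significant interaction and are still unsupported because both emotions are significant. The three-way step was not included here; it can only lower the support rates.

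**Step 3: does the rule give too much false support?**

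With no true effect and the two-way step, one outcome gives false support in about 2-3% of trials (1.8%, 2.1% and 2.8% for 2, 3 and 6 emotions). With a uniform shift of 0.3-0.8 SD and no emotion-specific effect it is 1.7-4.2%. Adding the three-way step brings the no-effect figure to about 0.6%. Choice among emotions therefore does not push the rate above 5% per outcome.

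For four outcomes joined by and/or, with no correction across them and the two-way step only, the rate is 6-11% with no effect and 6-18% with a uniform shift. If Holm covers the outcomes (modelled as a Bonferroni-level first step), it is 2-5%.

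**The case against.** The strongest reply is that the rule is already guarded. A three-way interaction comes first, then a two-way one; post-hoc tests are void if the global test fails; and Holm is named. This stands against a stronger reading that a reader might infer: that and/or, together with free choice of emotion, inflates false support to some 13-27%. Figures of that size are the chance that at least one of three to six interaction tests opens. They are not the chance that E1 is supported, which also needs the pattern and the three-way step. What remains of and/or is that the plan does not say whether Holm spans HbO and the behavioural measures.

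A second reply is that the loss depends on invented practice effects and on the number of emotions. That is fair. With six emotions and a 0.5 SD shift, support is still about 76%, and and/or gives a second route if one outcome shifts everywhere. The size is uncertain; the direction is not.

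A third reply is that E1 is exploratory and should not be tied to the second objective. That is also right. Section 9 says "We hypothesize that optimal priming stimulation will affect reaction times in an emotion-specific way", and condition 1 is sham-primed. So the documents do not support reading this as a flaw in a primary objective, or reaction time as the measure that must decide E1. Sad and happy are given only as examples, so sad minus happy need not be the sole contrast.

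None of these replies defends non-significance in other emotions as evidence that the change differs by emotion.

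**Conclusion.** The concern holds as a fault in the decision rule of E1 and E4. Under the stated assumptions, a common shift of 0.5 SD cuts support for a true 0.8 SD emotion-specific effect to about 42-76%, and a shift of 0.8 SD cuts it to about 8-24%, depending on whether there are two or six emotions. The test that answers the question stays at 92-96%. These figures rest on equal allocation, one outcome, correlation 0.5, and practice acting in the same direction as the effect.

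The fault is one of false rejection. The documents do not establish inflated false support; on that side there is only an undefined Holm family. Both hypotheses are exploratory, so the point is minor, and the primary resting-HbO tests are not touched.

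**What to change.** In E1 and E4, delete the requirement of non-significance in other emotions. Decide each hypothesis on the time-by-emotion interaction within the condition, as E2 and E3 are already decided on an interaction. Report the change in each emotion, and the differences between emotions, as estimates with confidence intervals.

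In the same edit, state that the existing Bonferroni-Holm adjustment covers the HbO and behavioural outcomes joined by and/or in E1, and list them. This belongs with the first change: once the interaction alone decides, each outcome carries 5% rather than 2-3%, and three independent outcomes without correction could reach 1 − 0.95³ = 14.3% before any three-way step. With Holm the total is at most about 5%.

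The cost is SAP wording only; data and model stay the same. The downside is that an effect seen in one outcome only must pass the Holm threshold. The change removes a practice shift that is equal across emotions. It does not separate stimulation from practice that itself differs by emotion, since each verdict remains within one arm.

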**10) Interventions:**

Number of Arms: 4

Allocation: Randomized

Enrollment Type: Anticipated

Number of Subjects: 80 participants with subclinical depression

Arm 1: Control

Arm Title: Priming sham TBS – followed by iTBS after an ISI of 0 minutes

Arm Description: self-explanatory, see Arm Title

Arm 2: Experimental

Arm Title: Priming cTBS – followed by iTBS after an ISI of 0 minutes

Arm Description: self-explanatory, see Arm Title

Arm 3: Experimental

Arm Title: Priming cTBS – followed by iTBS after an ISI of 10 minutes

Arm Description: self-explanatory, see Arm Title

Arm 4: Experimental

Arm Title: Priming cTBS – followed by iTBS after an ISI of 20 minutes

Arm Description: self-explanatory, see Arm Title

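### E4 is the only exploratory rule for an active-priming arm with no comparison against sham priming, so it can be met when the 20-minute arm behaves quite unlike sham

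*Combined protocol and SAP*

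**What the plan says.** Item 13 gives the rule: "Hypothesis E4 will be supported if there is a significant change in condition 4 in some (e.g. sad) but not other emotions" after stimulation, "following a post-hoc 2-way interaction between time and emotion". Nothing else is required. E1 uses the same criterion for condition 1, the sham-priming arm.

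The neighbouring rules bring in condition 1. For the 10-minute arm, "Hypothesis E3 will be supported if there is a significant interaction between time, emotion and conditions 3 and 1"; E2 has the same form for condition 2. For resting HbO in the 20-minute arm, H4 has two parts: a significant increase after stimulation, "but no significant difference in change scores between condition 1 and 4".

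Item 13 also has the three-way interaction of time, condition and emotion evaluated first. Post-hoc comparisons are declared nonsignificant if the global test is nonsignificant, and are left uncorrected if it is significant.

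The prediction for the 20-minute interval is in item 9 (Model Description): "20 minutes will have no effect (i.e., result in no difference, relative to sham priming". It belongs to this objective: "The first objective is to understand the effects of priming stimulation timing of the left DLPFC using fNIRS at rest". The two arms are defined in item 10. Condition 1 is "Arm Title: Priming sham TBS – followed by iTBS after an ISI of 0 minutes" and condition 4 is "Arm Title: Priming cTBS – followed by iTBS after an ISI of 20 minutes".

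**The concern.** Condition 4 receives priming cTBS followed by iTBS, and its participants do the same tasks twice. A pre/post change in that arm therefore contains the iTBS effect, practice and elapsed time, plus whatever the priming adds or removes. Condition 1 is the arm that allows the priming part to be separated, and E4 does not use it.

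E4 also ignores the direction of the change and does not require the same emotions to change as in condition 1. It can be met when condition 4 changes far more than sham, in the opposite direction, or in a different emotion. At stake is how the emotion results for the 20-minute arm are reported. A statement that E4 was supported would say nothing about whether 20-minute priming differs from sham priming, yet it would stand beside E2 and E3 verdicts that do make that comparison.

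**Working it through.** **1. The rules side by side (item 13)**

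| Rule | Arm | Outcome | Uses condition 1? |
|---|---|---|---|
| E2 | 2 (0 min) | task HbO, behaviour | yes, interaction contrast |
| E3 | 3 (10 min) | task HbO, behaviour | yes, interaction contrast |
| E4 | 4 (20 min) | task HbO, behaviour | no |
| H4 | 4 (20 min) | resting HbO | yes, second part |

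**2. Inputs.** From the documents: 80 participants, 4 arms, alpha 0.05, and the closed-test step. The plan gives no effect size, SD, power or margin, so it has no figure to reproduce. Assumed: equal allocation (80/4 = 20 per arm), two-sided tests, two emotions (sad, happy), change-score SD 1 for each, correlation r between a person's two changes of 0.3 to 0.7, no happy change in any arm, and one outcome at a time.

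**3. The rule as simulated (20,000 trials per scenario).** Let d be a person's sad change minus happy change, so SD(d) = √(2 − 2r): 1.18 at r = 0.3, 1.00 at r = 0.5, 0.77 at r = 0.7. E4 counts as supported if all three of these hold:
- the global three-way test is significant (one-way ANOVA of d over the four arms);
- d differs from 0 in condition 4 (time by emotion interaction);
- exactly one of the two emotions shows a significant change in condition 4.

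**4. Results.** Sad-emotion changes are in SD units for conditions 1, 2, 3 and 4. Ranges run over r = 0.3 to 0.7.

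| Scenario | Global test significant | E4 supported | 4-vs-1 contrast significant | E4 supported and 4-vs-1 not significant |
|---|---|---|---|---|
| Reversed: 0.8, 0, 1.2, −0.8 | 99.9–100% | 76–89% | 99–100% | about 0% |
| Much larger: 0.5, 0, 1.0, 1.5 | 95–100% | 90–95% | 74–98% | 2–21% |
| Equal to sham: 0.8, 0, 1.2, 0.8 | 77–99% | 59–89% | 5% | 57–85% |
| All arms alike: 0.8 each | 5% | 3–4% | 5% | 2–3% |

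**5. Analytic check of the 4-vs-1 column** (two-sample t, 38 df, noncentrality (difference/SD(d)) × √(20/2)). Reversed, r = 0.3: 1.6/1.18 = 1.35 SD, power 98.6%. Much larger, r = 0.3: 1.0/1.18 = 0.85 SD, power 74%; r = 0.7: 1.0/0.77 = 1.29 SD, power 98%. These agree with the simulation.

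**6. Reading the table.** In the first two scenarios the arms differ strongly and E4 is still usually supported. The global test asks whether any arms differ, not whether condition 4 resembles condition 1, so a deviant condition 4 helps it reach significance. The last column shows what an H4-style second part would do: support falls to 21% or less where condition 4 departs from sham, and hardly changes where it equals sham (59–89% to 57–85%).

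**7. What 20 per arm can show.** Power for a 4-vs-1 difference is 15% at 0.3, 34% at 0.5 and 69% at 0.8 SD of d. The 95% CI half-width is 2.024 × SD(d) × √(2/20): 0.76, 0.64 and 0.50 at r = 0.3, 0.5 and 0.7. A nonsignificant contrast is therefore weak evidence of similarity.

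**The case against.** The strongest objection concerns what E4 is meant to show. A reader might infer that the rule can return the opposite of what the protocol predicts. The documents do not go that far. The no-difference prediction is written for resting fNIRS, under the first objective. E4 concerns task HbO and behaviour, where item 9 makes no such prediction for 20 minutes, and the wording of hypothesis E4 is not in the documents (item 3 refers to a separate proposal). Carrying the prediction over is an inference. It is a reasonable one, because H4 treats the same arm in two parts and E4 repeats the criterion that E1 sets for the sham arm.

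A reader might also infer that the 4-vs-1 comparison is never made. That is too strong. Item 13 plans mixed models to find differences between conditions, with post-hoc pairwise comparisons, and a 4-vs-1 comparison fits within that. What is missing is its place in the E4 verdict.

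Third, E4 does not rest on condition 4 alone, since the global test uses all arms. That is correct, but the simulation includes this step and the weakness remains.

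Fourth, a mismatch might show up informally when E1 and E4 are read together. It would not show reliably: in the reversed scenario both arms have a sad-specific change of the same size, so both rules can be met.

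Finally, E4 is exploratory. That stands, and it limits the weight of the point.

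**Conclusion.** The point holds in this form: of the exploratory rules for the three active-priming arms, E4 alone makes no comparison with sham priming, and the closed-test step does not make up for it. Under the stated assumptions E4 is supported in about 76 to 89% of trials when condition 4 is opposite in sign to sham, and in about 90 to 95% when its change is 1.5 SD against 0.5 SD. The direct contrast would be significant in about 99 to 100% and 74 to 98% of trials respectively. These percentages rest on assumed effects, SD, correlation and allocation. That the rule lacks a comparator rests on the text alone.

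The documents do not support saying that E4 contradicts a stated prediction for the emotion outcomes, or that E4 seldom succeeds when condition 4 truly matches sham: in the equal-to-sham scenario it is supported in 59 to 89% of trials. The primary resting-HbO conclusion is not affected.

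**What to change.** Add the time by emotion by condition (4 vs 1) contrast from the planned mixed model to the E4 verdict, and report it with its 95% CI. Treat the change within condition 4 either as descriptive or as only the first part of a two-part rule, as in H4. State in the SAP what E4 predicts for the 20-minute arm relative to sham priming, so that the rule can be checked against it.

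A nonsignificant contrast should not be read as proof of no difference. Describe similarity to sham by the differences that the CI excludes, and call the result inconclusive if the CI is wide. A prespecified equivalence margin is optional for an exploratory hypothesis.

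The cost is SAP wording; no new data or model is needed. There are two limits. At 20 per arm the answer will often be inconclusive. And because the sham arm has a 0-minute interval, the contrast removes the shared iTBS and practice effects but not the 20 minutes of extra waiting in condition 4, which the report should say.

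### Exploratory hypothesis E6 is declared supported by a pre-post rise in recognition accuracy with no comparator, so a retest gain alone can meet the rule (minor)

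*Combined protocol and SAP*

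**What the plan says.** Section 13 (Statistical Analysis Plan) announces "two t-tests comparing ERA- recognition accuracies between subclinically depressed and control participants and between pre and post stimulation in the sample" of subclinically depressed participants; the second of these tests E6. The decision rule is: "Hypothesis E6 will be supported if recognition accuracy will be increased after stimulation compared to baseline in participants with subclinical depression". Neither sentence names a condition, whereas the rules for E1 to E4 each name theirs.

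Other relevant places in the same document:

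- Section 11, Outcome 3: reaction times and accuracy in the cognitive tasks are assessed both before and after stimulation.
- Section 10 (Interventions): 80 participants and four arms. All four arms receive iTBS; they differ in the priming (sham or cTBS) and in the interval before iTBS (0, 0, 10 and 20 minutes).
- Section 13, on behaviour and task HbO: "linear mixed models will be conducted to determine differences between conditions, followed by post-hoc pairwise comparisons". The support rules that follow use these models for E1 to E4.
- Section 13, on multiplicity: "The alpha level will be set at 0.05, adjusted for multiple comparisons using the Bonferroni-Holm procedure". The members of the Holm family are not listed.

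**The concern.** A pre-post change in a single group mixes any effect of the intervention with everything else that differs between the first and second testing. For an accuracy score from a repeated task, the obvious candidate is a retest gain from familiarity with the task. E6 has nothing to subtract this with. It makes no contrast between conditions, no arm goes without active iTBS, and the control sample is named only for E5, with no second measurement of it described.

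What is at stake is a statement in the results that E6 was supported, and that accuracy therefore rose because of stimulation, when the data would look the same had stimulation done nothing.

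**Working it through.** **No figure to reproduce.** The document gives no power calculation, SD, effect size or retest gain for recognition accuracy. The check therefore asks how often the rule is met when stimulation has no effect.

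**Inputs from the document.** n = 80 in four arms (section 10); one pre-post t-test and support on an increase (section 13); alpha 0.05 with Holm (section 13).

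**Assumptions.** Complete data; all arms pooled; two-sided testing; support requires a significant increase (the rule omits the word significant, but the t-test and alpha imply it). The retest gain dz = mean change / SD of change is varied from -0.1 to 0.4.

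**Formula.** T = mean change / (SD of change / √n). With a retest gain dz and no stimulation effect, T follows a noncentral t distribution with 79 degrees of freedom and noncentrality dz × √80 = 8.944 × dz. The chance of declaring E6 supported is P(T > critical value). For dz = 0.2 the noncentrality is 1.789 and the critical value at 0.05 is 1.990, which gives 42.4%.

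Three alpha levels are shown because the Holm family is not stated: 0.05 (no adjustment), 0.025 (first step if the family is E5 and E6) and 0.05/6 = 0.0083 (first step if it is E1 to E6).

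| Assumed retest gain dz | 0.05 | 0.025 | 0.0083 |
|---|---|---|---|
| -0.1 | 0.2% | 0.1% | <0.1% |
| 0 | 2.5% | 1.2% | 0.4% |
| 0.1 | 14.1% | 8.7% | 3.9% |
| 0.2 | 42.4% | 31.5% | 18.7% |
| 0.3 | 75.5% | 65.5% | 49.4% |
| 0.4 | 94.2% | 90.0% | 80.5% |

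The smallest observed gain that meets the rule is the critical value divided by √80: 1.990/8.944 = 0.22 SD of the change at 0.05, and 2.706/8.944 = 0.30 at 0.0083.

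**Comparison with a between-condition rule.** Simulation, 20 per arm (an equal split is assumed; the ratio is not stated), pre-post correlation 0.5, no stimulation effect. Post-stimulation accuracy adjusted for baseline is compared for conditions 2, 3 and 4 each against condition 1, two-sided, with Holm over the three contrasts. When the retest gain is the same in every arm, at least one contrast is declared in 4-5% of runs, whatever the gain between 0 and 0.4.

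Conditions 3 and 4 wait 10 and 20 minutes before iTBS, so their retest comes later and equal gain is itself an assumption. With unequal gains in conditions 1 to 4:

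| Gains (dz), conditions 1-4 | Any contrast declared | E6 rule at 0.05 |
|---|---|---|
| 0.4 / 0.4 / 0.3 / 0.2 | about 8% | about 81% |
| 0.4 / 0.4 / 0.2 / 0.0 | about 20% | about 60% |

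**The case against.** **E6 may be meant only as a change over time.** The document gives the test and the support rule but not the wording of E6 itself; section 3 refers to the ECS proposal for detail. If E6 claims only that accuracy is higher at the second testing, the rule fits it. This stands as a limit, and pooling over arms is likewise an inference, though the natural one. The remedy then is to say so in the SAP. The proposal may also specify parallel stimulus sets; these would reduce learning of particular items but would not supply a comparator.

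**The percentages depend on an assumed gain.** This is correct. Fatigue or a ceiling could make the drift zero or negative, and the rule would then rarely be met. The figures show what the rule does at a given gain; they are not expected error rates.

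**Holm adjustment protects.** It limits false positives due to chance. A retest gain is a real shift in the mean, so adjustment only raises the gain needed.

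**Stronger readings that the document does not support.**

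- A reader might infer that the plan leaves its second objective unanswered: "The second objective is to evaluate the effects of priming stimulation in the context of facial emotion processing and executive function in subclinical depression". It does not. E2 and E3 carry contrasts of conditions 2 and 3 with condition 1, using mixed models that cover behaviour. The fault lies in the E6 rule, which does not draw on them.
- A reader might set "Regarding the three exploratory hypotheses about" behaviour and task HbO against the six E hypotheses and conclude that the alpha for E6 is contradictory. That phrase introduces the mixed-model hypotheses; E5 and E6 come later, as separate t-tests. Only the unstated Holm family remains open.
- A reader might apply to E6 the rule that "post hoc comparisons will be declared nonsignificant if the global p value of the main- or interaction effect is nonsignificant". It is written for post-hoc comparisons after a GLM, and E6 is a stand-alone t-test.
- A reader might use condition 2 as a retest control, because the plan says "We hypothesize that 0 minutes will eliminate the effect of the test iTBS". That prediction belongs to the first objective, on fNIRS at rest. Nothing similar is predicted for recognition accuracy.

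**Conclusion.** The point holds as a minor one. As written, the E6 rule cannot separate a stimulation effect from a retest gain, because it is a single pre-post comparison in people who all receive iTBS. That conclusion follows from the design and needs no assumed number. Its size does: with no stimulation effect and 80 complete pairs, a gain of 0.2 SD of the change is enough for support in 42% of trials at 0.05 and 19% at 0.0083.

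It would be wrong to infer that the main results are compromised. E6 is exploratory, and hypotheses 1 to 4 on resting HbO do not depend on it. It would also be wrong to infer that adding a condition term rescues a claim about iTBS: with iTBS in every arm, such a term isolates priming only.

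**What to change.** 1. Replace the E6 support rule in section 13. Report the pre-post change in ERA accuracy, overall and per arm with 95% confidence intervals, as descriptive and not as evidence of a stimulation effect. This is enough on its own and costs only SAP wording: no participants and no new data.

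2. If E6 is to remain a test, compare post-stimulation ERA accuracy, adjusted for baseline accuracy, in conditions 2, 3 and 4 each against condition 1, with Holm over the three contrasts. Word it as an effect of priming only, and state that no arm separates iTBS itself from retest. This has three costs:
   - It answers a different question from a pre-post change.
   - Power is low. With 20 per arm and a correlation of 0.5 (both assumed), a true difference in one condition of 0.5 or 0.8 SD of change is detected about 27% or 66-67% of the time (24% or 61% at a correlation of 0.7).
   - Only condition 2 versus 1 is matched in timing. If retest gain falls with a longer interval, the error rate can exceed 5%: about 8% and 20% in the two unequal patterns under the working. The SAP should state this limit.

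3. If any test of E6 is kept, state which hypotheses share its Holm family.
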